### **Withdrawal of Consent:**

Participants who request to discontinue receipt of study treatment will remain in the study and must continue to be followed for protocol-specified follow-up procedures. The only exception to this is when a participant specifically withdraws consent for any further contact with him or her or persons previously authorized by the participant to provide this information. Participants should notify the investigator in writing of the decision to withdraw consent from future follow-up, whenever possible. The withdrawal of consent should be explained in detail in the medical records by the investigator, as to whether the withdrawal is only from further receipt of IP or also from study procedures and/or post treatment study follow-up and entered on the appropriate CRF page. In the event that vital status (whether the participant is alive or dead) is being measured, publicly available information should be used to determine vital status only as appropriately directed in accordance with local law.

### **7.3. Lost to Follow-up**

A participant will be considered lost to follow-up if he or she repeatedly fails to return for scheduled visits and is unable to be contacted by the study site.

The following actions must be taken if a participant fails to return to the clinic for a required study visit:

The site must attempt to contact the participant and reschedule the missed visit as soon as possible and counsel the participant on the importance of maintaining the assigned visit schedule and ascertain whether or not the participant wishes to and/or should continue in the study;

- Before a participant is deemed lost to follow-up, the investigator or designee must make every effort to regain contact with the participant (where possible, 3 telephone calls and, if necessary, a certified letter to the participant's last known mailing address or local equivalent methods). These contact attempts should be documented in the participant's medical record;
- Should the participant continue to be unreachable, he/she will be considered to have withdrawn from the study.

Discontinuation of specific sites or of the study as a whole is handled as part of [Appendix 1](#).

## **8. STUDY ASSESSMENTS AND PROCEDURES**

The investigator (or an appropriate delegate at the investigator site) must obtain a signed and dated ICD before performing any study-specific procedures.

Study procedures and their timing are summarized in the [SoA](#). Protocol waivers or exemptions are not allowed.

Immediate safety concerns should be discussed with the sponsor immediately upon occurrence or awareness to determine if the participant should continue or discontinue study intervention.

Adherence to the study design requirements, including those specified in the [SoA](#), is essential and required for study conduct.

All screening evaluations must be completed and reviewed to confirm that potential participants meet all eligibility criteria. The investigator will maintain a screening log to record details of all participants screened and to confirm eligibility or record reasons for screening failure, as applicable.

Every effort should be made to ensure that protocol-required tests and procedures are completed as described. However, it is anticipated that from time to time there may be circumstances outside the control of the investigator that may make it unfeasible to perform the test. In these cases, the investigator must take all steps necessary to ensure the safety and well-being of the participant. When a protocol-required test cannot be performed, the investigator will document the reason for the missed test and any corrective and preventive actions that he or she has taken to ensure that required processes are adhered to as soon as possible. The study team must be informed of these incidents in a timely manner.

For samples being collected and shipped, detailed collection, processing, storage, and shipment instructions and contact information will be provided to the investigator site prior to initiation of the study.

The total blood sampling volume for individual participants in this study is approximately 295 mL. The actual collection times of blood sampling may change. Additional blood samples may be taken for safety assessments at times specified by Pfizer, provided the total volume taken during the study does not exceed 550 mL during any period of 60 consecutive days.

## 8.1. Efficacy Assessments

Efficacy assessments for this study include measurements of HbA1c, fasting plasma glucose, and body weight which are covered in detail in [Section 8.2](#).

### 8.1.1. Primary Efficacy Parameter: HbA1c

HbA1c is the primary efficacy parameter for this study. See [Section 8.2.6](#) covering clinical laboratory tests.

### 8.1.2. Secondary CCI Efficacy Parameters

See [Section 8.2.6](#) (clinical laboratory assessments) for details regarding fasting plasma glucose. Participants achieving HbA1c <7% will be calculated based on HbA1c assessments as described in [Section 8.2.6](#).

See [Section 8.2.2](#) for details regarding assessment of body weight.

## 8.2. Safety Assessments

Planned time points for all safety assessments are provided in the [SoA](#). Unscheduled clinical laboratory measurements may be obtained at any time during the study to assess any perceived safety concerns.

### 8.2.1. Physical Examinations

Physical examinations are performed as indicated in the [SoA](#).

Physical examinations may be conducted by a physician, trained physician's assistant or nurse practitioner as acceptable and according to local regulation. A complete physical examination will include, at a minimum, assessments of the head, ears, eyes, nose, mouth, skin, heart and lung examinations, lymph nodes, and gastrointestinal, musculoskeletal and neurological systems.

Height will be measured at screening only.

A limited physical examination is performed at the follow up visit and may be performed at non-specified visits if there are findings during the previous physical examination or new/open AEs, if appropriate and at investigator discretion. The limited physical examination will be focused on general appearance, lungs, cardiovascular system, and participant reported symptoms.

Investigators should pay special attention to clinical signs related to previous serious illnesses.

### 8.2.2. Body Weight

Body weight will be measured in duplicate as indicated in the [SoA](#). The second weight measurement should be obtained at least 1-2 minutes apart from the first measurement.

Weight will be recorded using a calibrated scale (with the same scale used if possible for the duration of the study) reporting weight in either pounds (lb) or kilograms (kg), and accuracy to the nearest 0.2 lb (or 0.1 kg); ie, the device must be able to distinguish a difference between 150.4 lb (68.4 kg) versus 150.2 lb (68.3 kg). The scale must be placed on a stable, flat surface.

Weight measurement should be taken under the following conditions:

- While participant is in a fasted state (see [Section 5.3.1](#));
- After void of urine;
- After removal of shoes, bulky layers of clothing and jackets so that only light clothing remains;
- While remaining still during the measurement.

### 8.2.3. Vital Signs

#### 8.2.3.1. Blood Pressure and Pulse Rate

In this study, assessment of vital signs [systolic BP, diastolic BP, and pulse rate (PR)] will occur at the nominal time points specified in the [SoA](#) per the following specifications:

- At screening, the participant's arm circumference should be measured (eg, using a flexible anthropometric tape) at the midpoint of the length of the upper arm and the appropriate cuff selected and used throughout the study.
  - **Note:** Participants with arm circumference greater than the largest cuff size available at the site or >52 cm are not eligible. See [Section 5.2](#).
- BP and PR will be measured via an automated device using an oscillometric method (not auscultation).
  - Assessment of BP and PR can be manual (rather than using an automated device), only if an automated device is not available; however when done manually PR must be measured in the brachial/radial artery for at least 30 seconds.

- Supine BP and PR will be measured with the participant's arm supported at the level of the heart, and recorded to the nearest mm Hg, following a rest of at least 5 minutes. The assessment at Visit 3 (Day 1) will serve as the participant's baseline. Triplicate assessments will be measured at V3, V5, V7 and V9 with a brief interval (eg, 1-2 minutes) between successive triplicate assessments.
- Same arm (preferably the dominant arm) will be used for BP and PR assessments throughout the study, whenever possible.
- Participants should be instructed not to speak during BP and PR measurements.
- See [Appendix 9](#) for proposed chronology of procedures for nominal time points when vital sign assessments coincide with other procedures.

Additional collection times, or changes to collection times of BP and PR will be permitted, as necessary, to ensure appropriate collection of safety data.

#### **8.2.4. Electrocardiograms**

Standard 12-Lead ECGs should be collected at times specified in the [SoA](#) section of this protocol using an ECG machine that automatically calculates the heart rate and measures PR, QT, and QTcF intervals and QRS complex. Triplicate assessments will be measured at V3, V5, V7 and V9 with a brief interval (eg, 2-5 minutes) between successive triplicate assessments. All scheduled ECGs should be performed after the participant has rested quietly for at least 10 minutes in a supine position.

If a post dose QTcF interval remains  $\geq 30$  msec from the baseline **and** is a)  $>450$  msec; or b) an absolute QTcF value is  $\geq 500$  msec for any scheduled ECG for greater than 4 hours (or sooner, at the discretion of the investigator), or QTcF intervals get progressively longer, the participant should undergo continuous ECG monitoring. A cardiologist should be consulted if QTcF intervals do not return to less than the criterion listed above after 8 hours of monitoring (or sooner, at the discretion of the investigator).

In some cases, it may be appropriate to repeat abnormal ECGs to rule out improper lead placement as contributing to the ECG abnormality. It is important that leads be placed in the same positions each time in order to achieve precise ECG recordings. If a machine-read QTcF value is prolonged, as defined above, repeat measurements may not be necessary if a qualified medical provider's interpretation determines that the QTcF values are in the acceptable range.

ECG values of potential clinical concern are listed in [Appendix 7](#).

#### **8.2.5. Management of Glycemic Control**

Hypoglycemic adverse events (HAEs) and fasting plasma glucose will be routinely monitored during participation in the study.

Based on this information, as well as review of the results reported by the central laboratory, an assessment of any symptomatic and asymptomatic occurrence of hypo- or hyper-glycemia must be undertaken.

#### **8.2.5.1. Home Glucose Monitoring**

- To aide in management of their T2DM, all participants will be provided home glucose monitoring supplies including a Sponsor-provided glucometer, instructions on the use of the glucometer and accompanying supplies.
- Home glucose monitoring logs will be provided to participants for completion at home and brought to each outpatient visit to the site along with the glucometers. Investigators must review the home glucose monitoring logs completed by the participants and the readings stored in the glucometer device at each visit to the site after the placebo run-in visit (V2).
- Participants must perform home glucose monitoring at least 3 times weekly following at least an 8-(preferably 10-) hour fast (except water). However, the investigator may recommend more frequent home glucose monitoring if needed.
- Less frequent glucose monitoring will NOT be considered a protocol deviation unless the participant fails to monitor his/her glucose for 3 or more consecutive days.
- If the participant experiences symptoms of hypoglycemia, home glucose monitoring should be performed, and these symptoms, along with the glucometer measurement, should be captured on the home glucose monitoring log.
- If the participant uses his/her own glucometer, and not one provided by the Sponsor, a protocol deviation will NOT be recorded provided the investigator is still able to monitor the participant's daily glucose values according to the criteria stated above.

#### **8.2.5.2. Management of Hypoglycemia**

Any episode of hypoglycemia must be captured on the Adverse Event CRF with specific details captured on the Hypoglycemia Adverse Event Form CRF. For the definition of a hypoglycemic episode and severity categorization see [Section 8.2.5.2.1](#) below.

Participants noted to have a fasting glucose value (during home glucose monitoring) meeting the definition of hypoglycemia must be instructed to repeat the measurement the next day (following at least an 8 (preferably 10) hour fast, except water). If the second measurement also meets the below definition, participants must be asked to return to the site within 1 to 3 days (following at least an 8 (preferably 10) hour fast, except water) and have blood collected and sent to the central laboratory for analysis of fasting plasma glucose.

#### 8.2.5.2.1. Definition and Severity of Categorization of Hypoglycemic Adverse Event (HAE)

Based on review of the participant completed home glucose monitoring log at each site visit, as well as results reported by the central laboratory, the investigator must assess the glucose values as well as any symptoms documented.

HAE is defined as **one** of the following:

1. **Asymptomatic hypoglycemia:** An event *not* accompanied by typical symptoms of HAE but a blood glucose value of <70 mg/dL (3.9 mmol/L) using either glucometer (fingerstick blood glucose) or sponsor-identified central laboratory (plasma glucose);
2. **Documented symptomatic hypoglycemia:** An event during which typical symptoms of HAE are accompanied *with* a glucose value of <70 mg/dL (3.9 mmol/L) using glucometer (or sponsor-identified central laboratory) **and** the clinical picture includes prompt resolution with food intake, subcutaneous glucagon, or intravenous (IV) glucose;
3. **Probable symptomatic hypoglycemia:** An event during which symptoms of HAE are *not* accompanied by a glucose determination but was presumably caused by a blood glucose concentration of <70 mg/dL (3.9 mmol/L), **and** the clinical picture includes prompt resolution with food intake, subcutaneous glucagon, or IV glucose.

Each episode of HAE must be categorized with respect to severity. In order to characterize the event as severe, all **three (3)** criteria below must be met:

1. The participant was unable to treat him/herself. Neurologic impairment, and not the age of the participant, is the explanation for why the participant could not treat him/herself and required the assistance of another person.
2. The participant exhibited at least one of the following neurological symptoms:
  - Memory loss;
  - Confusion;
  - Uncontrolled behavior;
  - Irrational behavior;
  - Unusual difficulty in awakening;
  - Suspected seizure;
  - Seizure;

- Loss of consciousness.
3. Either:
- If blood glucose was measured and was  $\leq 54$  mg/dL (2.7 mmol/L) using glucometer (or central laboratory); or
  - If blood glucose was not measured, the clinical manifestations were reversed by oral carbohydrates, subcutaneous glucagon, or intravenous glucose.

Events that do not meet all the criteria above for severe HAE are characterized as mild or moderate in severity.

Any episode of HAE must be captured on the HAE CRF.

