### **8.2.5.3. Management of Hyperglycemia**

Hyperglycemia is defined as the following:

- Fasting glucose  $\geq 270$  mg/dL (15.0 mmol/L) using glucometer (or central laboratory).

After randomization, participants noted to have a fasting glucose value (during home glucose monitoring) meeting the above definition of hyperglycemia must be instructed to repeat the measurement the next day (following at least an 8 (preferably 10) hour fast, except water). If the second measurement also meets the above definition, participants must be asked to return to the site a day later (following at least an 8 (preferably 10) hour fast, except water) and have blood collected for fasting plasma glucose (and shipped to the central laboratory for analysis).

The investigator should determine if the participant collected the samples after an adequate fasting period; and if the participant is following recommended dietary guidelines. Proper dietary and collected procedures should be reinforced with the participant.

If the results from the central laboratory confirm the readings using glucometer, the participant should receive glycemic rescue medication at the discretion of the investigator (see [Section 6.5.5](#)).

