### **3.5.2. Hypoglycemic Monitoring**

Hypoglycemia AEs will be recorded in the AE Case Report Form (CRF) with details of the event captured on the Hypoglycemic Event Details CRF. Details of when these will be recorded are given in the protocol Section 8.2.5.2.

For programming purposes, the hypoglycemic AE categories are based on the following:

- Severe Hypoglycemia: Severe is checked in the severity criteria of the CRF. This assessment will be made by the PI based on the protocol definition.
- Documented Symptomatic Hypoglycemia: If (1 – Did the participant have symptoms of hypoglycemia?) Yes and (2 – Was the blood glucose measured?) Yes and result <70 mg/dL on the CRF, but hypoglycemia is not classified as severe.
- Asymptomatic Hypoglycemia: If (1) No and (2) Yes and result <70 mg/dL on the CRF, but hypoglycemia is not classified as severe.
- Probable Symptomatic Hypoglycemia: If (1) Yes and (2) No and (2b – If blood glucose was not measured, did symptoms resolve when treated with carbohydrate or glucagon?) Yes on the CRF, but hypoglycemia is not classified as severe.

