### 3.5.3.2. Clinical Laboratory Parameters of Interest

For the specific laboratory parameters listed in the table below, the following endpoints will be derived:

- Abnormalities defined as either a “Flag Level” or “Alert Level” as in the table below

Parameter	Flag Level	Alert Level	Conventional Units
Fasting Plasma Glucose	< 70	≤ 54	mg/dL
	≥ 270	≥ 270	
Amylase	>ULN	Pfizer standard flag for PCC	U/L
Lipase	>ULN	Pfizer standard flag for PCC	U/L
Calcitonin	>ULN	Pfizer standard flag for PCC	pg/mL

Alanine Aminotransferase	$\geq 2$ ULN	Pfizer standard flag for PCC	U/L
Aspartate Aminotransferase	$\geq 2$ ULN	Pfizer standard flag for PCC	U/L
Alkaline Phosphatase	$\geq 2$ ULN	Pfizer standard flag for PCC	U/L
Gamma Glutamyl Transferase	$\geq$ ULN	Pfizer standard flag for PCC	U/L
Total Bilirubin	$> 1.5$ ULN	Pfizer standard flag for PCC	mg/dL
Serum Total Bile Acids	$>$ ULN	Pfizer standard flag for PCC	$\mu$ mol/L

PCC – potential clinical concern

ULN – upper limit of normal as determined by the central laboratory

These endpoints will be derived using both pre and post-dose data separately. Post-dose will include all post-baseline data including unplanned readings and pre-dose will include all data from the placebo run-in defined by including all values from Visit 2 to pre-dose, including the baseline measurement and unplanned readings. Note, both pre- and post-dose populations will be from the safety analysis set (defined in Section 4).

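### The severe-hypoglycemia glucose limit is printed as 54 mg/dL and 2.7 mmol/L, but 54 mg/dL is 3.0 mmol/L, so the mmol/L figure can under-grade an event

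*Protocol*

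**What the plan says.** Protocol section 8.2.5.2.1 defines a hypoglycemic adverse event (HAE) and then grades it. The definition uses "a blood glucose value of <70 mg/dL (3.9 mmol/L") as its threshold.

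A severe grade needs all three of the following:

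1. Neurologic impairment left the participant unable to self-treat and in need of another person's help.
2. At least one listed neurological symptom was present.
3. If glucose was measured, it was at or below 54 "mg/dL (2.7 mmol/L) using glucometer (or central laboratory"). If it was not measured, the manifestations were reversed by carbohydrate, glucagon or intravenous glucose.

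The consequence of missing any one criterion is explicit: "Events that do not meet all the criteria above for severe HAE are characterized as mild or moderate in severity".

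Section 8.2.5.3 sets the hyperglycemia limit at 270 "mg/dL (15.0 mmol/L) using glucometer (or central laboratory").

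On the analysis side, SAP section 3.5.2 defines the severe category this way: "Severe is checked in the severity criteria of the CRF. This assessment will be made by the PI based on the protocol definition". Symptomatic events with a measured "result <70 mg/dL on the CRF, but hypoglycemia is not classified as severe" go to the documented symptomatic category. SAP section 3.5.3.2 lists flag and alert levels in mg/dL only: "Fasting Plasma Glucose < 70 ≤ 54 mg/dL". SAP section 6.6.1.2 lists HAEs and summarizes them by category, with no test.

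**The concern.** Criterion 3 presents two numbers as one limit, and they do not convert into each other. The mmol/L figure is the stricter of the two. A grader who works from it will call some events mild or moderate that the mg/dL figure makes severe.

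Such an event is clinically important by construction: the participant was neurologically impaired and needed someone else's help. The SAP states no rule that would recover the grade from the recorded glucose. The event would therefore be counted as documented symptomatic instead of severe. Where severe events are rare, moving one can change what an arm's safety summary says. Safety and tolerability is a stated secondary objective, and Protocol section 6.5.5 allows sulfonylureas as rescue on top of randomized treatment. Section 4.2 names that class among the agents that can cause hypoglycemia alongside a GLP-1 receptor agonist.

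The protocol prints both units, and its BMI criterion refers to sites in North America, Europe and Asia. Meters are not fully standardized either: "If the participant uses his/her own glucometer, and not one provided by the Sponsor, a protocol deviation will NOT be recorded", provided that the investigator can still monitor the values. Neither document says which unit any site or meter uses.

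**Working it through.** **Inputs.** There are three distinct glucose pairs in the protocol: 70 mg/dL with 3.9 mmol/L (section 8.2.5.2.1), 270 with 15.0 (section 8.2.5.3, and again as 270 with 15 in exclusion criterion 18), and 54 with 2.7 (section 8.2.5.2.1, criterion 3).

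**Step 1: factor implied by each pair** (mg/dL ÷ mmol/L).

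| Pair | Implied factor |
|---|---|
| 70 / 3.9 | 17.95 |
| 270 / 15.0 | 18.00 |
| 54 / 2.7 | 20.00 |

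Only the criterion 3 pair departs from about 18.

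**Step 2: try to reproduce the printed mmol/L values at 18.0.**

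- 70 / 18.0 = 3.89, printed 3.9: reproduces.
- 270 / 18.0 = 15.0, printed 15.0: reproduces.
- 54 / 18.0 = 3.00, printed 2.7: does not reproduce.

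Using the protocol's other implied factor, 54 / 17.95 = 3.01. No rounding gives 2.7.

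**Step 3: reverse conversion.** 2.7 × 18.0 = 48.6 mg/dL, and 2.7 × 17.95 = 48.5 mg/dL.

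**Step 4: width of the gap.** 3.0 − 2.7 = 0.3 mmol/L; 54 − 48.6 = 5.4 mg/dL. Compared exactly, whole-number readings of 49 to 54 mg/dL pass the mg/dL limit and fail the mmol/L limit (49 / 18.0 = 2.72). On a meter showing mmol/L to one decimal, the affected displays are 2.8, 2.9 and 3.0. A value of 49 mg/dL would display as 2.7 and pass, so on such a meter the band starts at 50 mg/dL (50 / 18.0 = 2.78).

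**Step 5: effect on classification.** Take an event that meets criteria 1 and 2 with a measured glucose of 2.9 mmol/L (2.9 × 18.0 = 52.2 mg/dL).

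| Limit applied | Criterion 3 | Grade | SAP 3.5.2 category |
|---|---|---|---|
| ≤54 mg/dL | met | severe | severe |
| ≤2.7 mmol/L | not met | mild or moderate | documented symptomatic |

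**Step 6: how often this could arise.** Protocol section 2.2.2.1 reports one participant with hypoglycemia, graded mild, among 98 randomized in the earlier 28-day study: 1 / 98 = 1.02%. If the same proportion held here, 400 × 1/98 = 4.1 participants would have any hypoglycemia. If instead the rate were constant over time, the 112 treatment days give 4.1 × (112 / 28) = 16.3. Both figures are assumptions built on a single event pooled over active and placebo. They count any hypoglycemia; severe events inside the band would be a small part of them.

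**The case against.** The strongest reply is that this is a slip in a parenthesis with almost no practical reach. The mg/dL figure leads, and the SAP works only in mg/dL. Few or no events should land in the band. Hypoglycemia management in Protocol section 8.2.5.2 is triggered by the 70 mg/dL definition, which converts correctly, and the discontinuation criteria in section 7.1.1 do not use the severe limit. Every episode also goes on the AE form, where Appendix 3 asks for a separate intensity rating. An event such as a convulsion would usually be handled as serious. A misgraded event would therefore not vanish from the safety data.

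All of that is fair, and it keeps the point small. It does not make the criterion consistent. The HAE-specific severe category rests on the investigator's reading of this text, and the text offers two limits.

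A second reply is that the under-grading direction assumes 54 mg/dL was intended. The only support inside the documents is the SAP's fasting plasma glucose alert level, which is a different rule. If 2.7 mmol/L were intended, the mg/dL figure would over-grade instead. This stands as a reason to have the sponsor confirm the value. Either way, one of the two printed numbers is wrong.

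**Conclusion.** The concern holds. Criterion 3 contains two limits 0.3 mmol/L (5.4 mg/dL) apart, and neither document resolves them. The arithmetic rests only on the conversion factor in the protocol's own other pairs. That 54 mg/dL is the intended value is likely but inferred from the SAP's alert level.

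The effect is confined to events that meet criteria 1 and 2, have a measured glucose in the band, and are graded on the mmol/L figure. Events without a glucose measurement are untouched. The total HAE count does not change; an affected event only moves from severe to documented symptomatic. HAEs are summarized descriptively, so no efficacy estimate, hypothesis test or power figure is affected. The expected number of affected events is few or none. The correction is still worth making, because this is an operative safety-grading rule and the error is certain.

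**What to change.** Amend criterion 3 in Protocol section 8.2.5.2.1 to read ≤54 mg/dL (3.0 mmol/L), after the sponsor's clinical team confirms that 54 mg/dL is the intended limit. If they intended 2.7 mmol/L, correct the mg/dL figure instead, to about 48.6 mg/dL (49 in whole numbers). Put the same pair in the HAE CRF completion instructions. For data already collected, re-check the severity grade of any HAE recorded with a glucose above 2.7 and up to 3.0 mmol/L (about 49 to 54 mg/dL).

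The cost is a one-line protocol clarification, a CRF completion note, and a severity query for each HAE in the band, if there are any.
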